1. LIST OF ABBREVIATIONS

AE	Adverse event
ARTI	Acute Respiratory Tract Infections
BAL	Bronchoalveolar lavage
CA-ARTI	Community acquired acute respiratory tract infections
CRP	C Reactive Protein
COVID-19	Coronavirus Infectious Disease 2019
DALY	disability adjusted life years
eCRF	electronic Case Report Form
ETA	Endotracheal Aspirate
Dx	Diagnostics
EQ5D	EuroQoL (Europe Quality of Life) 5 dimensions
ER	Emergency Room
GCP	Good Clinical Practice
GDPR	General Data Protection Regulation
ICD	International Classification of Diseases
ICF	Informed Consent Form
LAR	Legally Accepted Representative
LRTI	Lower Respiratory Tract Infections
NPS	Nasopharyngeal swabs
PCT	Procalcitonin
POCT	Point of Care Testing
PP	Pneumonia Panel (Biofire®Filmarray®)
PPAS	Point Prevalence Audit Study
RP2.1 plus	Respiratory Panel version 2.1 plus (BioFire®FilmArray®)
RSDT	Rapid syndromic diagnostic testing
SAE	Serious adverse event
SARS-CoV-2	Severe Acute Respiratory Syndrome Coronavirus 2
SOP	Standard Operating Procedures
WP	Work Package

2. SUMMARY

Background and Rationale: Community-acquired acute respiratory tract infections (CA-ARTI) are among the most frequent infectious diseases worldwide. At the same time, uncomplicated acute respiratory infections (ARI) is the most frequent cause of inappropriate antibiotic use. Antibiotic resistance rates are related to antibiotic use in any setting, but opportunities to implement a more judicious antibiotic prescribing are probably most apparent in primary care and emergency departments. Optimal clinical management of CA-ARTI is hampered because of diagnostic delays and suboptimal test sensitivity, leading to incorrect or missing etiologic diagnosis, and over prescription of antibiotics. Highly sensitive molecular assays have increased the detection of respiratory pathogens, but the **impact in clinical decision-making** needs further evaluation. Accurate and rapid identification of infected patients allows for more rational and effective infection control practices and public health responses which will limit morbidity and mortality, economic damage, and can allow low risk/non-infected and recovered people to return to the workforce.

Objective: To assess the impact of rapid diagnostic testing of patients with Acute Respiratory Tract Infection (ARTI) at the emergency department, on (1) hospital admission rates and (2) antibiotic prescriptions (days of treatment) and (3) the non-inferiority in terms of clinical outcome. Geographical and seasonal variation will be assessed on a real time basis including pathogens of public health interest. The impact will be stratified within age groups and risk factors in order to determine the long-term clinical, public health and economic determinants for the integration of diagnostics in a global and sustainable perspective.

Study design: Prospective, multi-center, individually randomised, controlled trial.

Study population: Adults (≥ 18 years old) consulting in selected participating sites with CA-ARTI.

Study Intervention: The diagnostic intervention is rapid syndromic testing with:

- BioFire FilmArray Pneumonia Panel plus (PP): Sputum (and/or ETA or BAL sample)
- BioFire FilmArray Respiratory Panel 2.1 plus (RP2.1plus): Nasopharyngeal swab

Main study parameters/endpoints:

- Days alive out of hospital (superiority endpoint), within 14 days
- Days on Therapy (DOT) with antibiotics (superiority endpoint), within 14 days
- Adverse outcome (non-inferiority safety endpoint)
 - For initially non-admitted patients: any admission or death within 30 days
 - For initially hospitalised patients: i) any readmission, ii) ICU admission ≥ 24 hours after hospitalisation, or iii) death within 30 days

Nature and extent of the burden and risks associated with participation, benefit and group relatedness: Participation in the study involves collection of data that can be obtained from medical charts and follow up questionnaires and interviews. Respiratory samples (e.g. nasopharyngeal swab, sputum) will be obtained as standard of care and diagnostic intervention (Biofire FilmArray) will be used only for participants randomised to the intervention. Based on the results of diagnostic testing (BioFire FilmArray) antibiotics may be withheld when deemed unnecessary, or a different antibiotic class may be selected when certain bacterial pathogens are detected. The risks and benefits of management decisions, complemented with adequate training, are subject to the current investigation.

3. GENERAL CONSIDERATIONS WORK PACKAGE 4 AND VALUE-Dx OVERVIEW

The purpose of VALUE-Dx consortium (www.value-dx.eu) is to facilitate and accelerate the rigorous assessment and implementation of (new) diagnostic technologies into healthcare settings, by establishing the infrastructure, methods, processes and approaches needed to understand, evaluate, assess, and demonstrate the multi-faceted value of diagnostics and overcome the associated barriers to their widespread adoption and use. VALUE-Dx focuses its research on **community acquired acute respiratory tract infections (CA-ARTI)**.

The objectives of VALUE-Dx are:

- To design a health-economic framework to assess and demonstrate the value of diagnostics both for individual patients and for public health impact by reducing antibiotic use and subsequent antibiotic resistance among patients;
- To establish a sustainable European Standardised Care Network adequately trained and resourced to conduct clinical trials evaluating the value of diagnostics;
- To design and implement clinical studies to demonstrate the value of diagnostics in the optimal management of CA-ARTIs;
- To explore, define and attempt to resolve the psychological, ethical and social barriers which prevent the more widespread adoption of diagnostics delivering healthcare to the population.

The clinical studies, to be implemented in WP4, aim to gather evidence on:

- i) doses or days of antibiotics prescribed,
- ii) proportion of patients not receiving antibiotics;

WP4 studies will be performed separately in primary care and long-term facilities (WP4a)- POCT with Abbott and BD and Emergency Rooms (WP4b)- Rapid syndromic diagnostic testing with bioMérieux.

The clinical trial will align – where possible with the other WPs of the project.

- WP1 aims to develop evidence-based clinical algorithms that integrate point of care tests. Initial analysis has provided results on accuracy of the selected groups of items: signs and symptoms, biomarkers, imaging and rapid diagnostic tests, for prediction of influenza and bacterial pneumonia, respectively.
- WP2 will explore analytical performance of some tests in the trials and will collect pathogen and host biomarker data.
- WP3 will provide data management.
- Within WP4a, during the winter season from January to March 2020, a web-based point prevalence audit survey (PPAS) on presentation and management of CA-ARTI in primary care and long-term facilities was performed. The aim is to retrospectively characterize patients who

seek healthcare for CA-ARTI, quantify antibiotic prescriptions and to benchmark patterns of diagnostic in different European countries.

- WP5 is setting-up data collection for health economic modelling, that includes a disease model, diagnostic models and antibiotic resistance predictions. The variables to be included to assess direct and indirect medical costs and quality of life need to be collected in the clinical trials of WP4.
- WP4b, The ADEQUATE study is an individual randomised study that aims to assess the impact of rapid syndromic diagnostic testing (Biofire® bioMérieux) in patients with Acute Respiratory Tract Infection (ARTI) at the emergency department, on (1) hospital admission rates and (2) antimicrobial prescriptions (days of treatment) and (3) the non-inferiority in terms of clinical outcome.
- The ADEQUATE study is composed of an adult and a paediatric part, both with their own protocol, but with a joined sample size calculation and Statistical Analysis Plan (SAP). The study analysis will include both the adult and paediatric populations.
- The current protocol describes the trial of WP4b for the adult population.

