7. STUDY DESIGN AND DURATION

7.1. Study design and justification

This is a prospective, multi-centre, **individually randomised controlled open-label trial**. Approximately 1600 patients will be randomised in the trial in up to 10 investigational sites in the European region. Patients will be followed at day 14 and day 30 after randomisation. In a subset of patients, follow up will be extended to time points 3 and 6 months.

Enrolment will be competitive across sites.

Justification of the design. The aim is to deliver a study outcome that is **valid** (absence of bias), **precise** (sufficiently powered to achieve clinically relevant absence and presence of difference), and **generalizable** (recognizable population). The study needs to be **feasible** in terms of costs

(determined by number of study sites and number of tests to be performed), with an easy patient enrolment and an achievable burden on laboratories in both adult and paediatric sites. Therefore, although an **individually randomised trial** - in contrast to cluster randomisation - requires informed consent from all recruited patients fulfilling inclusion criteria prior to performing the test. This approach has several advantages: 1. Internal validity of the trial is guaranteed by the randomisation, whereas in cluster-randomised trials, patient selection criteria can be difficult to apply in a consistent manner, inducing a risk of selection bias; 2. Required sample size is lower compared to a cluster-randomised trial; 3. Recognizable population can be realized, although generalizability will always be lower compared to enrolling all-comers; 4. Feasibility: compared to a cluster-randomised trial, a lower sample size is needed, reducing costs for study execution; fewer hospitals, fewer patients, and a lesser burden on labs because tests are only performed in 50% of enrolled patients instead of 100% of all-comers. Moreover, although requirement of informed consent to be obtained at the ER could be considered as a drawback of this design, it in fact may help in enrolling the pursued patient population for this specific trial. We aim for patients in which the result of the rapid syndromic testing can guide clinical decision making. This implies that there is also time for obtaining informed consent.

In choosing the primary endpoints the following considerations were made:

- The composite endpoint is designed to capture the relevant outcomes and will be combined for analysis

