13. STATISTICAL CONSIDERATIONS

13.1. Sample size calculation

Co-primary endpoints used in the study:

1. Days on antibiotic treatment within 14 days (superiority endpoint)
2. Days alive out of the hospital within 14 days (superiority endpoint)
3. Adverse outcome within 30 days (non-inferiority safety endpoint)

Required sample sizes are presented for endpoint 2 and 3. Endpoint 1 is non-limiting due to having an expected smaller standard deviation compared to endpoint 2 and having the same clinically relevant effect size.

The intervention is considered successful if superiority is demonstrated for either or both endpoints 1 and 2 AND non-inferiority is demonstrated for endpoint 3. We use a hierarchical nested design: superiority primary endpoints are tested first. Only if superiority to at least one of the two superiority endpoints is confirmed, the non-inferiority safety endpoint is taken into consideration. To maintain an overall alpha < 0.05, the two superiority endpoints will be tested using a two-sided alpha of 0.025, while the non-inferiority endpoint will be tested using a one-sided alpha of 0.05. The minimal power for the superiority endpoints is set to 0.9 and for the non-inferiority endpoint to 0.95. This is to maintain overall power of the trial, given the hierarchical testing. For 'Adverse outcome' we considered different non-inferiority margins. For 'Days on antibiotic treatment' and 'Days alive out of the hospital' we defined 1 day as a clinically relevant effect size.

The distribution of endpoint 2 is yet unknown for the ARI population. We supported our sample size calculation using data of patients presenting with CAP to Dutch ERs and hospitalised to a non-ICU ward (ClinicalTrials.gov: NCT02604628). The standard deviation (SD) of 'Days alive out of the hospital within 14 days' in this population was 4 days. The theoretical maximum SD with a 14 days follow-up period is 7 (which would be the case if 50% had zero days and 50% had 14 days alive out of the hospital). However, we expect that in the target population the variability for this endpoint will be less than in the CAP population. We varied the SD to assess the impact on

the sample size. We used a standard correction factor of 1.15 for non-normality of the data. (Table 1) Hence for the superiority endpoints a sample size of 457 per arm would be adequate.

Table 1: Sample sizes for Days alive out of the hospital using different assumptions

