SD	Relevant effect size	Alpha	Beta	Correction	Sample size per arm
3	1	0.025	0.1	1.15	257
4	1	0.025	0.1	1.15	457
5	1	0.025	0.1	1.15	714
6	1	0.025	0.1	1.15	1,028
7	1	0.025	0.1	1.15	1,399

For adverse outcome, if we assume an incidence of 10% the sample size would be 780 per arm, and if we assume 5% it would be 412, in both cases using a non-inferiority margin of 5% (Table 2). A high power for adverse outcome is considered important because both the superiority and the non-inferiority hypothesis need to be confirmed in order to declare the intervention a success so a total of 780 adults per study arm would be required to reach 95% power

Table 2: Sample sizes for adverse outcome using different assumptions.

Incidence *	Non-inferiority margin	Alpha**	Beta	Sample size per arm
0.05	0.05	0.05	0.05	412
0.10	0.05	0.05	0.05	780

* same for intervention and control arm; ** one-sided alpha

To account for potential drop-outs we will aim for a **total of 1600 adults** in the study. The sample size includes participants that are randomised and does not include enrolled but non-randomised patients.

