13.2. Analysis populations

A statistical analysis plan will be prepared after protocol approval and once site selection process has been initiated.

The main analyses will be performed for the total population

Analyses will be stratified by:

- age groups (i.e. 18-49, 50-65, >65)
- clinical syndrome: exacerbation of chronic pulmonary disease, influenza-like illness, laryngitis/laryngotracheitis (croup), acute bronchitis
- risk factors. Patient groups at risk for developing severe disease are well known, such as the elderly, patients with chronic pulmonary, cardiovascular or metabolic disease or immunocompromised patients. Clinical predictors of severity are also well known. Still,

within risk groups may exist the uncertainty whether to hospitalise and/or to treat and the impact of testing may be assessed.

- Vaccination status. Influenza. Pneumococcal.

The primary analysis will follow the intention-to-treat principle in which groups are compared based on the allocated regimen. In the per protocol analysis we will exclude participants not receiving the test according to the randomised regimen (e.g. randomised to rapid syndromic testing but not receiving the test).

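### Does the joint adult and paediatric wording in section 3 leave the population for the co-primary tests open?

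*Combined protocol and SAP*

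**What the plan says.** Section 3 explains that ADEQUATE has an adult and a paediatric part. Each has its own protocol, but "with a joined sample size calculation and Statistical Analysis Plan (SAP". It adds: "The study analysis will include both the adult and paediatric populations". The next bullet sets the scope of this document: "The current protocol describes the trial of WP4b for the adult population".

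Section 13.1 gives one calculation. On the non-inferiority endpoint it concludes that "a total of 780 adults per study arm would be required to reach 95% power", and it sets a total of 1600 adults to allow for drop-out. The success rule reads: "The intervention is considered successful if superiority is demonstrated for either or both endpoints 1 and 2 AND non-inferiority is demonstrated for endpoint 3". It names no population.

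Section 13.2 says: "The main analyses will be performed for the total population". The term is not defined. A list of strata follows directly, with age bands that begin at 18. The primary analysis is by intention to treat, and the SAP is still to be prepared. The models in section 13.3 contain no term for adult versus child.

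**The concern.** Section 3 promises a joint calculation, and section 13.1 shows one with no paediatric number, event rate or standard deviation. The sentence on the study analysis can mean a single pooled analysis or two analyses under one SAP. A total population could then mean all randomised adults, or adults plus children. Two further details suggest text shared with the paediatric protocol: section 13.2 lists croup among the syndromes, and section 7.1 refers to "an achievable burden on laboratories in both adult and paediatric sites".

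The non-inferiority test is where this would matter. The 5-point margin, 10% incidence and 95% power appear in a calculation that concludes for adults. A pooled test controls the one-sided 5% error for the average risk difference over both groups. If the excess of adverse outcomes were larger in adults than in children, adult non-inferiority could be inferred too easily from the pooled result.

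**Working it through.** **1. The plan's own figures, adults only.** Inputs from section 13.1: equal incidence p in both arms, margin 0.05, one-sided alpha 0.05, power 0.95, so both normal quantiles are 1.645.

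n per arm = 2p(1-p)(1.645 + 1.645)² / 0.05²

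- p = 0.05: 411.2, rounded up to 412, as stated.
- p = 0.10: 779.2, rounded up to 780, as stated.

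Superiority on days alive out of hospital: n = 1.15 × 2 × (SD × (z for two-sided 0.025 + z for power 0.90) / 1 day)². SD of 3, 4, 5, 6 and 7 gives 257, 457, 714, 1,028 and 1,399, all as stated.

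Drop-out: 2 × 780 = 1560, and 1560/1600 = 0.975. The total of 1600 is therefore 780 per arm with an implied 2.5% allowance (780/0.975 = 800). Adults account for all of it.

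Adult non-inferiority power at p = 0.10 is Φ(0.05/√(2 × 0.10 × 0.90/n) - 1.645):

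- n = 780: 95.0%.
- n = 800: 0.05/0.015 - 1.645 = 1.688, giving 95.4%.

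**2. What the sections say about the population.** The summary gives the study population as adults. Section 3 limits this protocol to adults. Sections 8.1 and 8.2 admit only patients aged 18 or over. Section 13.1 counts adults. The age bands in section 13.2 start at 18. On the other side stand one sentence and one adjective in section 3, the croup entry and the mention of paediatric sites. In section 13.2 the total population stands directly above a list of strata, so its ordinary meaning is everyone randomised under this protocol, as opposed to the subgroups.

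**3. What pooling could do.** The documents give no paediatric figures, so all of these are assumptions: 80 to 800 children per arm, paediatric control risk 3% to 10%, and paediatric excess d of 0 to 7.5 points. Adults are placed at the margin (10% versus 15%) with 800 per arm.

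With c children per arm and n = 800 + c, RD = (800 × 0.05 + c × d)/n, SE = √((p0(1-p0) + p1(1-p1))/n) from the pooled arm risks p0 and p1, and P(pass) = Φ((0.05 - RD)/SE - 1.645).

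Worked cell (c = 200, control risk 5%, d = 0):

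- RD = 40/1000 = 0.04; p0 = 90/1000 = 0.09; p1 = 130/1000 = 0.13.
- SE = √((0.0819 + 0.1131)/1000) = 0.01396.
- (0.05 - 0.04)/0.01396 - 1.645 = -0.929, giving about 17.6%.

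Chance of passing the non-inferiority test, nominal 5%:

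| Excess in children | 80 per arm | 200 | 400 | 800 |
|---|---|---|---|---|
| 0 | 9% | 17-18% | 36-41% | 72-84% |
| 2.5 points | 7% | 10% | 15-17% | 29-36% |
| 5 points (as adults) | 5% | 5% | 5% | 5% |
| 7.5 points | 4% | 2% | 1% | 0.2-0.4% |

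These are upper bounds on declaring non-inferiority, because sections 7.1 and 13.1 consider that endpoint only after superiority is shown on at least one other. They also use a crude risk difference, where section 13.3 plans an adjusted Cox model with bootstrapped intervals.

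**The case for a change.** The strongest case for a change is that the population behind a success verdict should not have to be inferred. An explicit sentence in section 3 says that the analysis covers both groups, and two statisticians could run different primary analyses and each cite the protocol. The trial is open label and its verdict depends on a safety non-inferiority test, so the choice should be fixed before data are seen. A few words would do it, with no extra patients and no loss of adult power.

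Part of this stands. The section 3 wording does not match what section 13.1 displays, and section 13.2 would read better with its population defined. The rest does not carry. A joint calculation can mean shared endpoints, alpha, margin and method, with each protocol reporting its own number; the explicit count of adults in section 13.1 fits that reading. A pooled test would hold its 5% for the pooled difference. It becomes anti-conservative only when the result is then claimed for adults and the excess in children is smaller. Averaging over age bands within the adults raises the same issue. Requiring adult non-inferiority as well, or making any combined analysis merely supportive, is a choice of estimand on which reasonable statisticians differ.

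**Conclusion.** No change to the plan is needed. No stated figure is wrong: 412, 780 and 1600 all follow from the stated inputs without any children. Read in the way that nearly all of the protocol supports, the adult analysis has 95.0% to 95.4% power at 10% incidence and keeps its nominal error. The gap is one of wording, of a kind that analysts fill sensibly: the joint SAP was still to be written, and naming the analysis sets is its ordinary task.

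The possible inflation runs from none, or even a conservative test, to a large one, depending wholly on assumed paediatric numbers and effects. It also needs a pooled confirmatory test followed by an adult claim, which no section describes. This conclusion rests on the adult reading. The paediatric protocol and the joint SAP are not among the documents, so how they describe the combined analysis could not be checked.

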4. BACKGROUND AND RATIONALE

4.1. Background

Community-acquired acute respiratory infections (CA-ARTI), including upper and lower respiratory tract infections, are among the most frequent infectious diseases worldwide. Lower respiratory tract infections (LRTI) are among the most lethal communicable diseases and the fourth cause of death globally, responsible for an estimated 3 million deaths in 2016 [1]. LRTI disproportionately affects children younger than 5 years and is the second cause of disability adjusted life years (DALYs). A study published in the Lancet in 2018 estimated the global, regional, and national morbidity, mortality, and aetiologies of LRTI in 195 countries, between the years 1990–2016. In 2016, LRTI caused 652,572 deaths (95% uncertainty interval 586,475–720,612) in children younger than 5 years, 1,080,958 deaths (943,749–1,170,638) in adults older than 70 years, and 2,377,697 deaths (2,145,584–2,512,809) in people of all ages, worldwide. *S. pneumoniae* was the leading cause of LRTI morbidity and mortality globally, contributing to more deaths than all other aetiologies combined in 2016 (1,189,937 deaths (690,445–1,770,660)[2], particularly as community acquired pneumonia. Within the European region, geographical variations are present. Over the years, the epidemiology has changed due to changing populations, with increased disease burden in elderly (>70 years) in many regions, varying prevalence of smoking and varying patterns of vaccine usage [3, 4].

On the other hand, uncomplicated ARTI is the most frequent cause of inappropriate antibiotic use [5, 6], and there is a need of more judicious antibiotic prescription to prevent exposure to drug-related adverse events, selection of antibiotic resistance and emergence of opportunistic pathogens that substitute the indigenous microbiota. At the same time, the clinical role of bacteria whose normal ecological niche is in the airways is an unresolved issue because of contamination with oropharyngeal flora. Antibiotic resistance rates are related to antibiotic use in any setting, but opportunities to decrease unnecessary treatments are probably most apparent in primary care and emergency departments. Not only the ecological but also, the economic cost of antimicrobial

resistance per antibiotic consumed is considerable [7-9]. Management is heterogeneous in diverse geographical areas due to non-uniform guidelines, both for diagnostic and antimicrobial stewardship [10].

One of the major challenges in clinical decision-making is the absence of microbiological evidence of the aetiological agent in CA-ARTI at the time the antibiotics must be initiated so rapid diagnostic testing may have an impact. The required sample is not always available, and with conventional testing there may be low sensitivity (40-60% cases without aetiological diagnosis) and an important diagnostic delay before results are available. An accurate and reliable distinction between bacterial and viral causes of CA-ARTI would provide an important opportunity for better antimicrobial stewardship. However, due to substantial overlap in clinical disease presentation and laboratory parameters it is currently impossible to reliably distinguish viral from bacterial aetiology based on available tools.

It has been proposed that implementation of Point-of-Care tests (POCT) with biomarkers or microbiological tests to differentiate viral from bacterial infections may reduce inappropriate antibiotic prescriptions [11]. There is encouraging evidence from randomised trials for biomarker-guided antimicrobial management. In a multicenter study in adults in primary care the combination of selected clinical symptoms with the addition of C-reactive protein (CRP) measurement improved diagnostic information, but measurement of procalcitonin (PCT) did not add clinically relevant information [12]. In a Cochrane review of controlled trials of biomarkers in patients with CA-ARTI, PCT appeared to be more informative than CRP and other inflammatory markers, as it was associated with an earlier increase upon infection, a better negative predictive value, and was influenced by immunosuppressive medication [13].

The development of highly sensitive molecular assays has increased the detection of respiratory pathogens in patients with CA-ARTI, and increased our understanding of the role of viruses in CA-ARTI [14]. However, diagnostic methods that detect a virus do not always rule-out bacterial infection. Additional diagnostic yield has been demonstrated by using molecular tests but evidence is limited regarding the impact on antibiotic use or costs [15-17].

In this context, a new molecular rapid syndromic testing platform (BioFire; Salt Lake City, UT, USA) might improve clinical decision-making in patients with CA-ARTI. The BioFire FilmArray Pneumonia Panel plus (PP) is a multiplexed nucleic acid amplification test that identifies 34 bacterial and viral targets, including antimicrobial resistance genes from sputum or bronchoalveolar lavage (BAL) specimens. The BioFire FilmArray Respiratory Panel 2.1 plus (RP2.1plus) can simultaneously detect 24 viruses and atypical pathogens from nasopharyngeal swabs. Both panels allow syndromic testing and results can be provided in less than one hour with high sensitivity and specificity [18, 19]. Several single-center studies have reported promising results and ongoing clinical trials are summarized in section 9.2. Additional data is needed to prospectively assess the impact of rapid syndromic testing in daily clinical decision-making as well as to determine its costs and effects.

The emergence of severe acute respiratory syndrome coronavirus 2 (SARS-CoV-2) [20] has had an unprecedented and dramatic impact on the health care system and on the world economy. One of the most effective tools in the management of this global pandemic is the ability to rapidly and accurately test patients with signs and symptoms of ARTI or with risk factors for exposure. Some countries have used aggressive and widespread testing paired with contact tracing to manage the crisis and have been apparently the most successful at reducing mortality rates, the

strain on the health care system and the spread of the virus. Expanding testing locations could prevent patients from spreading infections due to lack of availability of testing outside hospitals and by reducing the time between sample collection and test result.

